The 1-hour PPG increment endpoint will be analysed using the FAS and the in-trial observation period based on a multiple imputation technique where the change from baseline in 1-hour PPG increment at week 16 for subjects withdrawn from trial are imputed based on data from completers in the NovoRapid® arm. Multiple copies (100 copies) of the full dataset will be generated by imputing missing values based on estimated parameters as follows:

- An analysis of variance model with strata (two levels based on use of own CGM or not), previous insulin use (three levels: NovoRapid[®], Apidra[®], Humalog[®]), and region as factors and baseline 1-hour PPG increment as covariate is fitted to the change from baseline in 1-hour PPG increment at week 16 for the NovoRapid[®] group only. The estimated parameters, and the variance, from this model are used to impute missing values using stochastic simulation at week 16 for subjects in both treatment groups in order to generate 100 complete datasets.
- For each of the complete data sets, the change from baseline to week 16 is analysed using an analysis of variance model with treatment, strata (two levels based on use of own CGM or not), previous insulin use (three levels: NovoRapid[®], Apidra[®], Humalog[®]), and region as factors, and baseline 1-hour PPG increment as covariate.
- The estimates and standard deviations for the 100 data sets are pooled to one estimate and associated standard deviation using Rubins formula. From this, the pooled estimates and 95% confidence interval for the treatment difference is calculated.

The superiority will be assessed by comparing the upper limit of the 95% CI to 0. If the upper 95% CI is below 0 then superiority will be confirmed.

Change from baseline in HbA_{1c} 16 weeks after randomisation (Step 3)

As the third step in the hierarchical testing, superiority of HbA_{1c} 16 weeks after randomisation with faster-acting insulin aspart compared to NovoRapid[®] is to be confirmed.

The confidence interval from the primary analysis 1) will be used to determine superiority. Superiority will be confirmed if the upper boundary of the two-sided 95% confidence interval of the mean treatment difference (faster-acting insulin aspart minus NovoRapid[®]) is below 0%.

Change from baseline in 1,5-anhydroglucitol 16 weeks after randomisation (Step 4)

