For endpoints measured over time, mean values will be plotted to explore the trajectory over time. For survival endpoints (e.g. drop-out pattern) Kaplan-Meier plots are presented for each treatment.

Data collected before randomisation (Visit 6) will only be summarised descriptively.

Subjects that prematurely discontinue from treatment or withdraw from trial will attend end of treatment visits called visit 22A and 22B. Data collected at these visits will be reallocated to the next scheduled visit where the given assessment is planned. As a general rule, all observed values from randomised subjects will be used in all statistical analyses, but in case two different values are associated to the same visit in time, the use of a given value will depend on the estimand of interest. For the primary estimand the reallocated on-treatment value will not be used and for the secondary estimand the reallocated on-treatment value will be used. The estimands will be defined in the next section.

Testing strategy and estimands

The primary objective, to confirm the effect of CSII treatment with fast-acting insulin aspart in terms of glycaemic control by comparing it to CSII treatment with NovoRapid[®], in adults with T1DM, will be assessed by the change from baseline in HbA_{1c} using a non-inferiority approach.

More specifically the upper limit of the 95% confidence interval for the difference between fast-acting insulin aspart and NovoRapid[®] should be compared to a non-inferiority margin of 0.4%. If it is below or equal to 0.4% non-inferiority will be considered established and effect demonstrated.

The trial also aims to compare CSII treatment with fast-acting insulin aspart to NovoRapid[®] for a number of confirmatory secondary endpoints. The family-wise type I error rate will be controlled in the strong sense using a hierarchical (fixed sequence) testing procedure for the primary estimand. This is based on a priority ordering of the null-hypotheses, and testing them in this order using the two-sided 95% confidence interval approach until an insignificant result appears. The effect is that rejection of a null hypothesis only will be considered for analyses where all previous null-hypotheses have been rejected in favour of fast-acting insulin aspart.

The steps in the hierarchical testing procedure are as follows:

Step 1 (Primary analysis): HbA_{1c} non-inferiority of fast-acting insulin aspart versus NovoRapid[®]

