The 1-hour PPG increment endpoint will be analysed using the FAS and the in-trial observation period based on a multiple imputation technique where the change from baseline in 1-hour PPG increment at week 16 for subjects with missing value are imputed based on data from subjects in the NovoRapid[®] arm with non-missing values at week 16. Multiple copies (100 copies) of the full dataset will be generated by imputing missing values based on estimated parameters as follows:

- An analysis of variance model with strata (two levels based on use of own CGM or not), previous insulin use (three levels: NovoRapid[®], Apidra[®], Humalog[®]), and region as factors and baseline 1-hour PPG increment as covariate is fitted to the change from baseline in 1-hour PPG increment at week 16 for the NovoRapid[®] group only. The estimated parameters, and their variances, from this model are used to impute missing values using stochastic simulation at week 16 for subjects in both treatment groups in order to generate 100 complete datasets.
- For each of the complete data sets, the change from baseline to week 16 is analysed using an analysis of variance model with treatment, strata (two levels based on use of own CGM or not), previous insulin use (three levels: NovoRapid[®], Apidra[®], Humalog[®]), and region as factors, and baseline 1-hour PPG increment as covariate. The estimates and standard deviations for the 100 data sets are pooled to one estimate and associated standard deviation using Rubin's formula. From this, the pooled estimate and 95% confidence interval for the treatment difference are calculated.

The superiority will be assessed by comparing the upper limit of the 95% CI to 0. If the upper 95% CI is below 0 then superiority will be confirmed.

Change from baseline in HbA_{1c} 16 weeks after randomisation (Step 3)

The third step in the hierarchical testing is to confirm superiority of fast-acting insulin aspart compared to NovoRapid[®] with respect to HbA_{1c} 16 weeks after randomisation.

The confidence interval from the primary analysis 1) will be used to determine superiority. Superiority will be confirmed if the upper boundary of the two-sided 95% confidence interval of the mean treatment difference (fast-acting insulin aspart minus NovoRapid[®]) is below 0%.

Change from baseline in 1,5-anhydroglucitol 16 weeks after randomisation (Step 4)

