For each Subject this is calculated as the total number of infusion sets used divided by the actual duration of the randomised treatment period in days, multiplied by seven. It will be summarised for each treatment using descriptive statistics.

Number of Subjects with at least one non-routine change categorised by reasons for change

The percentage of Subjects with at least one non-routine change will be presented, categorised by reasons for change, in a frequency table by treatment.

3 Changes to the statistical analyses planned in the protocol

General considerations

It has been clarified how data collected at visit 22A and 22B are handled.

Statistical analysis

It has been clarified that type 1 error will only be controlled for the primary estimand.

In the sensitivity analysis 2) for change from baseline in HbA_{1c} it has been clarified that baseline HbA_{1c} is still included in the analysis as a covariate.

In the statistical analysis in the protocol it is not clear if missing values or values for subjects discontinuing treatment/withdraw from trial should be imputed. Some of the following changes have been implemented to account for this issue.

In the sensitivity analysis for change from baseline in HbA_{1c} it has been changed from subjects withdrawing from trial to subjects with an imputed value at week 16 to be aligned with the primary analysis.

In the statistical sensitivity analysis 3b) for change from baseline in HbA_{1c} copy reference has been changed to conditional imputation, and for 3c) jump to reference has been changed to unconditional imputation to clarified the method used.

It has been clarified that the statistical analysis 4) will be repeated as for the confirmatory secondary endpoints.

For change from baseline in 1-hour PPG increment (meal test) it has been clarified how the endpoint is derived, which is aligned with the other endpoints derived from the meal test. To align with the primary analysis it has been changed so values at week 16 are imputed for subjects with missing values instead of imputing values for subjects withdrawn from trial, and the imputations are based on subjects in the NovoRapid[®] arm with non-missing values instead of completers in the NovoRapid[®] arm.

For the statistical analysis of change from baseline of time spent in low IG (≤ 3.9 mmol/L) it has been clarified that the corresponding baseline value will be included as covariate.

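### As SAP section 2 most naturally reads, a lone on-drug Visit 22A meal test, however early, serves as the week-16 value in the step 2 de facto analysis

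*SAP*

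**What the plan says.** SAP section 2, General considerations, deals with subjects who stop treatment early or leave the trial. For Visits 22A and 22B: "Data collected at these visits will be reallocated to the next scheduled visit where the given assessment is planned". Keeping observed data is the default: "As a general rule, all observed values from randomised subjects will be used in all statistical analyses". An exception is made where values compete: "in case two different values are associated to the same visit in time, the use of a given value will depend on the estimand". The sentence after that reads: "For the primary estimand the reallocated on-treatment value will not be used". Under the secondary estimand the choice goes the other way.

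The flow chart and Protocol Table 8-2 place the scheduled meal tests at Visit 6 (baseline) and Visit 22 (week 16). The flow chart adds one at Visit 22A. Protocol 8.1.8.1 and 8.1.8.2 ask that the 22A test be done on randomised product unless safety prevents it.

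For step 2, SAP 2.4.1 says that week-16 changes "for subjects with missing value are imputed based on data from subjects in the" NovoRapid arm who have week-16 data. The primary estimand, which section 2 repeats for the 1-hour PPG increment, is the week-16 difference whether or not the subject stayed on treatment.

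**The concern.** The mapping rule has no time limit. A meal test done on drug in, say, week 3 by someone who then leaves the trial goes to week 16. No second value displaces it, and nothing is missing, so nothing is imputed. The analysis then treats an early on-drug response as the outcome at week 16, when the subject may have been off the product for months.

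HbA1c is less exposed. It is also measured at weeks 4, 8 and 12, so an early 22A value goes to one of those visits and week 16 is imputed.

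Three groups could be affected:
- trial withdrawers who did the 22A meal test;
- retained discontinuers who miss the Visit 22 meal test;
- possibly subjects whose 22A falls after week 12.

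Step 2 is confirmatory, has 80.0% marginal power and gates steps 3 to 5. At stake are the size of its estimate and whether two programmers would build the same step 2 dataset.

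**Working it through.** **Path through the rules**
1. A 22A value goes to the next visit where the assessment is planned. For the meal test that is always Visit 22.
2. All observed values are used. The choice by estimand is introduced for the case of two values on one visit, and the barring sentence most naturally completes that case.
3. With one value there is no choice to make, and SAP 2.4.1 imputes only missing values. The 22A value stands.
4. A retained discontinuer who does have a Visit 22 meal test is unaffected, because the later value is used.

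**The late group.** Protocol 8.1.8.1 is not consistent here. One rule has a 22A held more than 12 weeks after randomisation replace Visit 22. Other text in the same section schedules CGM at Visit 22 for those stopping between Visits 14 and 20, and CGM and 7-7-9 profiles at Visit 22 for those stopping between Visits 20 and 22. If Visit 22 is held with a meal test, two values exist and the two-value rule already drops the on-drug one. The size of this group is open until the passages are reconciled.

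**Inputs (SAP 2.1).** Difference 0.9 mmol/L in absolute value, SD 3.4, 225 per arm, two-sided 5%. Treatment discontinuation might be as low as 4%, half of it (2%) trial discontinuation.

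**Plan's own figure.** SE = 3.4 × √(2/225) = 0.3206. Noncentrality = 0.9/0.3206 = 2.81 with 448 df. The noncentral t distribution gives power 80.0%, as stated.

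**Upper bound on the shift.** Let w be the share of the faster aspart arm with a lone on-drug 22A value. Assume each shows the full 0.9 effect at 22A and none at week 16. Shift = w × 0.9.
- w = 2% (4.5 of 225, trial withdrawers): 0.018 mmol/L; 0.018/0.3206 = 0.056 SE.
- w = 4% (9 of 225, every discontinuer): 0.036 mmol/L; 0.036/0.3206 = 0.112 SE.
- Each further percentage point adds at most 0.009 mmol/L.

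**Power if these values are imputed from NovoRapid instead.** The expected difference becomes 0.9 × (1 − w). With SE held at 0.3206, power is 78.4% at 2% and 76.7% at 4%. That ignores imputation variance. A rough allowance treats imputed values as lost sample size: SE = 3.4 × √(2/(225 × (1 − w))).

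| w | Difference | SE | Power |
|---|---|---|---|
| 1.5% | 0.8865 | 0.3230 | 78.2% |
| 2% | 0.882 | 0.3238 | 77.6% |
| 3% | 0.873 | 0.3255 | 76.3% |
| 4% | 0.864 | 0.3272 | 75.0% |

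The 1.5% and 3% rows are the shares at or before week 12 if discontinuations spread evenly over 16 weeks (an assumption): 12/16 = 75% of 2% and of 4%. The powers in the table are approximations, not bounds.

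**The case against.** The strongest reply is that the barring sentence carries no condition of its own. Read alone, it excludes the reallocated on-treatment value from the primary estimand in every case, and there is nothing to correct. That reading is possible. It sits badly with the preceding sentence, which uses all observed values and opens an exception only for two values on one visit, and SAP section 3 merely records that 22A and 22B handling has been clarified. The ambiguity remains and is itself a reason for one more sentence.

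A second reply is that taking the Visit 22 value when it exists, and the observed 22A value otherwise, is a coherent order of preference. This stands in part: the rules do not contradict each other. But coherence does not make an on-drug value from an earlier week a measure of week 16 regardless of discontinuation.

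A reader might also infer that the SAP removed a clear protocol safeguard, since Protocol 17.4.1 says week-16 values "for subjects withdrawn from trial are imputed based on data from completers in" the NovoRapid arm. The documents do not support this. The same protocol text goes on to say that the model estimates "are used to impute missing values using stochastic simulation at week 16 for subjects in both treatment groups", so it speaks both of withdrawn subjects and of missing values. SAP section 3 says of the protocol that "it is not clear if missing values or values for subjects discontinuing treatment/withdraw from trial should be imputed". Protocol 18.4 retains end-of-treatment visit data for the report without saying how they map to week 16.

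**Conclusion.** The point holds on the natural reading of SAP section 2, and it is minor. At the planned rates the shift is at most 0.018 to 0.036 mmol/L, towards faster aspart if there is an on-drug benefit.

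Those bounds assume that every affected subject attended 22A on drug, had the full 0.9 mmol/L effect there and has none at week 16. The 4% case also assumes that no retained discontinuer has a Visit 22 meal test, although Protocol 8.1.8.1 keeps them on the key visits. The true shift is probably smaller: consent withdrawers are only encouraged to attend (Protocol 6.6.2), on-drug testing has a safety exception, and the test requires a pre-meal SMPG of 4.0 to 8.8 mmol/L (Protocol 8.3.7). Discontinuation above the planned 4% would raise the ceiling.

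A reader might infer that the rule could produce a false superiority claim. It does not follow: with no treatment difference, an on-drug 22A value carries no advantage and there is no shift. The issue is the size of the estimate, not type I error.

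**What to change.** Add to SAP section 2: for the primary estimand of the meal-test endpoints, a reallocated on-treatment 22A value is not used as the week-16 value even when it is the only value; week 16 is then missing and is imputed from the NovoRapid arm as in section 2.4.1. Leave the two-value rule and the secondary-estimand rule as they are.

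Reconcile the statements in Protocol 8.1.8.1 on whether Visit 22 is held after a late 22A. If 22A values after week 12 are kept in the main analysis because that visit replaces Visit 22, add one step 2 sensitivity analysis that treats them as missing too. That cut-off would come from the visit rule, not from the estimand.

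The cost is a short SAP addition, a change to visit mapping and possibly one extra analysis. No new data are needed for treatment discontinuers: Protocol 8.1.8.1 already has the eCRF confirm whether the 22A meal test was done on trial product. A few more values are imputed, and step 2 power falls from 80.0% to approximately 78.2% if 1.5% of values are imputed and 76.3% if 3% are. If late values are dropped as well, the same approximation gives 77.6% at 2% and 75.0% at 4%.

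Separately, as an editorial point, Protocol 8.5.1.3 mentions a meal test at Visit 14 that neither the flow chart nor Table 8-2 shows.

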2.1 Sample size calculation

The primary objective of the trial is to confirm the effect of CSII treatment with fast-acting insulin aspart in terms of glycaemic control by comparing it to CSII treatment with NovoRapid[®] in adults with T1DM, using a non-inferiority approach. The non-inferiority margin of 0.4% (absolute) was chosen as described in section 5.2.1 of the protocol. The statistical evaluation will be done as described in section [2.3](#).

The trial also aims to confirm superiority of CSII treatment with fast-acting insulin aspart for a number of secondary confirmatory endpoints using the hierarchical testing procedure as described in section [2](#) (General considerations).

The sample size is determined to ensure sufficient power for the first step and second step in the hierarchical testing procedure.

In previous exploratory trials where CSII treatment with faster aspart has been investigated, the completion rates have been high. Therefore it is expected that treatment discontinuation might be as low as 4% where trial discontinuation constitutes half of these.

The power for the non-inferiority step is based on a t-statistic under the assumption of a one-sided test of size 2.5 %. A mean treatment difference of -0.1% for the comparison between fast-acting insulin aspart and NovoRapid[®] is expected. As trials in this population where Subjects are using insulin pumps and where data from treatment withdrawn subjects is retrieved are limited, a conservative estimate of the standard deviation (SD) in change from baseline in HbA_{1c} of 0.8% was chosen.

For determination of power in the second step in the hierarchical testing, where change from baseline in 1-hour PPG increment 16 weeks after randomisation is compared between fast-acting insulin aspart and NovoRapid® a t-statistic with a two-sided test of size 5.0% is used, where the treatment difference is expected to be at least 0.9 mmol/L [16 mg/dL]. The SD=3.4 mmol/L [62 mg/dL] in change from baseline in 1-hour PPG increments 16 weeks after randomisation based on laboratory analysed plasma glucose (PG) in a standardised meal test is considered reasonable, based on prior trials.

The power calculation is done using proc power in SAS Version 9.4. Please refer to [Table 2-1](#) for assumption of the sample size calculation.

Table 2-1 Specifications assumed for sample size calculation

	Statistical test	Significance Level	Analysis Population	Non-inferiority Margin	SD	Mean Difference	Randomisation Scheme
Step 1	2-group t-test	One-sided 2.5%	FAS	0.4% (absolute)	0.8	-0.1	1:1
Step 2	2-group t-test	Two-sided 5.0%	FAS	NA	3.4	0.9	1:1

In [Table 2-2](#), the sensitivity of the sample size to the power in Step 1 and Step 2 is shown for three different sample sizes of FAS. Three different choices of the mean difference are used to calculate the power in Step 2.

Table 2-2 Sensitivity of sample size to power in step 1 and step 2

N Total FAS	N per arm FAS	Step 1			Step 2			
		Mean Diff	SD	Step 1 Power (%)	Null Diff	Mean Diff	SD	Step 2 Power (%)
300	150	-0.1	0.80	>99.9	0	0.8	3.4	52.8
		-0.1	0.80	>99.9	0	0.9	3.4	62.7
		-0.1	0.80	>99.9	0	1.0	3.4	71.9
450	225	-0.1	0.80	>99.9	0	0.8	3.4	70.2
		-0.1	0.80	>99.9	0	0.9	3.4	80.0
		-0.1	0.80	>99.9	0	1.0	3.4	87.6
600	300	-0.1	0.80	>99.9	0	0.8	3.4	82.0
		-0.1	0.80	>99.9	0	0.9	3.4	89.9
		-0.1	0.80	>99.9	0	1.0	3.4	94.9

In conclusion, a sample size of 450 Subjects in the FAS (225 Subjects per group) will ensure a power of >99.9% to conclude HbA_{1c} non-inferiority in the first step. This sample size gives 80.0% marginal power to conclude 1 hour PPG increment superiority in the second step.

Assuming a screening failure rate of 24% and run-in failure rate of 11%, 666 Subjects should be screened for inclusion in the trial.

2.2 Definition of analysis sets

The following analysis sets are defined in accordance with the ICH-E9 guidance:¹

- Full Analysis Set (FAS) includes all randomised Subjects. In exceptional cases, randomised Subjects may be excluded from the FAS. In such cases, the reason for exclusion will be justified and documented. Subjects in the FAS will contribute to the evaluation “as randomised”
- Per Protocol (PP) Analysis Set includes all Subjects in the full analysis set, excluding Subjects who:
 - Have violated any inclusion criteria
 - Have fulfilled any exclusion criteriaSubjects in the PP set will contribute to the evaluation “as treated”
- Safety Analysis Set includes all Subjects receiving at least one dose of the IMP or its comparator. Subjects in the safety analysis set will contribute to the evaluation “as treated”.

Randomised Subjects who are lost to follow-up, and where no information on exposure to the trial product or its comparator is available after randomisation, will be handled as unexposed.

Before data are released for statistical review, a blinded review of all data will take place to identify serious non-adherence to the protocol that may potentially affect the results. Furthermore, extreme values and outliers will be identified by the statistician during programming and data review, according to ICH-E9.¹ This will be performed using a fake randomisation.

The Subjects or observations to be excluded, and the reasons for their exclusion must be documented and signed by those responsible before database lock. The Subjects and observations excluded from analysis sets, and the reason for this, will be described in the clinical trial report (CTR).

